10.14.1 Study Exit

A Study Exit eCRF is required for all subjects. Prior to exiting a subject from the study, it is recommended to follow the subject until all ongoing related AEs are resolved or unresolved with no further actions planned. Upon exiting from the study, no further study data will be collected, or study visits will occur for the subject. All data available through the time of the subject's exit will be used for analysis.

Subjects are urged to remain in the study as long as possible but may be exited from the study for any of the following situations:

- Subject lost to follow-up
- Subject death
- Subject did not meet inclusion/exclusion criteria
- Subject was not implanted with an investigational device
- Subject did not provide consent or data use protection authorization
- Subject chose to withdraw (e.g., consent withdrawal, relocation to another geographic location)
- Investigator deemed withdrawal necessary (e.g., medically justified, failure of subject to maintain adequate study compliance)
- Device explant with no planned replacement.

The following information should be collected at study exit:

- Date of exit
- Reason for exit

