10.3 Scheduled Follow-up Visit Windows

Should a subject miss a visit or the visit falls outside the pre-specified window, a study deviation must be reported, and the original follow-up schedule maintained for subsequent visits.

Data analyses include follow-up visits, regardless of whether the visit occurs within the window. Therefore, a late visit is preferred over a missed visit but must be accompanied with a reported study deviation. Follow-up visit windows are listed in Table 5 and are based on days post-implant.

Table 5: Study Follow-up Visit Windows

Study Follow-up Visit	Window (Calculated calendar days post-implant; implant is Day 0)		
	Window Start (days post-implant)	Target (days post-implant)	Window End (days post-implant)
7-Day Post-Procedure Follow-up Visit	4 days	7 days	10 days
1-Month Follow-up Visit	20 days	30 days	40 days
2-Month Follow-up Visit	46 days	60 days	74 days
3-Month Follow-up Visit	76 days	90 days	104 days
6-Month Follow-up Visit	150 days	180 days	210 days
12-Month Follow-up Visit	330 days	360 days	390 days
24-Month Follow-up Visit	660 days	720 days	780 days

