10.11 Assessment of Safety

All adverse events and device deficiencies (see Section 12) will be collected throughout the study once the informed consent form is signed until the subject is exited from the study.

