12.3 Processing Updates and Resolution

For any changes in status of a previously reported adverse event or DD (i.e., change in actions taken, change in outcome, change in relatedness), information needs to be updated on, or added to the original AE or DD eCRF. All AEs must be followed until the AE has been resolved, is unresolved with no further actions planned, the subject dies or exits the study, or until study closure, whichever occurs first.

In the event that a subject is exited from the study prior to their completion in the study, it is recommended to continue following the subject until all unresolved related AEs, are resolved or unresolved with no further actions planned

At the time of study exit, all collected adverse events that are unresolved must be reviewed and an update to the original AE must be reported.

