## 7.10 Safety Evaluation

All AEs and DDs will be collected throughout the study once the informed consent form is signed. AEs and DDs will be coded using the most recent version of Medical Dictionary for Regulatory Affairs (MedDRA). Severity will be assessed by the Investigator. Relatedness and seriousness of the events will be classified by the Investigator, CEC, and the Sponsor. Cases where the Investigator's classification does not match the CEC's classification will be displayed within the final report; however, the CEC's adjudication will be used for data analysis.

Adverse events that occur prior to implant will be summarized. Adverse events that occur on or after tibial neuromodulation implant date through study discontinuation will also be summarized; summaries specific to the timeframe from implant to the 6-month follow-up visit will be included as well as those that include all post-implant follow-up (i.e. though "24 months"). AE tables summarizing adverse device effects (ADE) will also be included. ADE are events deemed related to the neurostimulator, procedure, external device, study aids, or therapy. In addition to tables of overall ADE, summaries by the individual relatedness component will be summarized using the following categories: procedure-related, device-related (neurostimulator/external device), therapy-related, and study aids-related. Resolution (number of events/percentage) of ADE will be summarized using similar time groupings to other summaries. ADE will also be summarized grouping the events by Common Terminology Criteria for Adverse Events (CTCAE) grade.

The denominator for post-implant summaries will be the number of subjects in the All Implanted analysis set, while for pre-implant summaries it will include all enrolled subjects. Events occurring on date of implant will be considered post-implant events.

Summaries of serious adverse events (SAEs) will also be completed in similar ways to AE summaries. Unanticipated Serious Adverse Device Effects (USADE) will be described. Adverse events in subjects with implant attempted but without full implant will also be summarized as part of additional AE summary tables of the Full Analysis Set. Device-related deaths and system modifications will be summarized in detail.

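### A subject whose first implant attempt fails may be exited with no minimum observation period and no clearly required post-procedure contact, so procedure-related events that start after exit would not be collected

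*Protocol*

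**What the plan says.** **Exit and collection (Protocol)**
- Section 10.14.1 includes "Subject was not implanted with an investigational device" among the reasons for exit. No minimum time is attached, and screen failures are not separated from failed attempts.
- The same section states the consequence: "Upon exiting from the study, no further study data will be collected, or study visits will occur for the subject".
- Section 10.11 says that adverse events and device deficiencies "will be collected throughout the study once the informed consent form is signed until the subject is exited from the study".
- Two safeguards are given as recommendations. Section 10.14.1: "Prior to exiting a subject from the study, it is recommended to follow the subject until all ongoing related AEs are resolved" or need no further action. Section 12.3, for early exit: "it is recommended to continue following the subject until all unresolved related AEs, are resolved or unresolved with no further actions planned".

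**Visits and contacts (Protocol)**
- Section 10.3: "Follow-up visit windows are listed in Table 5 and are based on days post-implant". This covers the 7-day post-procedure visit.
- Section 10.14 places the duty of follow-up to 24 months on implanted subjects.
- Table 4 footnote a requires a 7-day visit and a 1-month call after system modification or explant procedures. Section 10.8 requires a 1-month call before exit when a device is explanted and not replaced.
- Section 10.1 and Table 4 footnote f recommend a check-in call within about 48 hours of each study visit. Section 10.1 introduces these calls as following device implant.

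**Analysis**
- SAP 7.1.3 defines the FAS by attempted implant and names it the primary set for safety as well as effectiveness.
- SAP 7.10 says "Adverse events in subjects with implant attempted but without full implant will also be summarized", in additional FAS tables. The denominator of its post-implant tables is the All Implanted set.
- Protocol 14.9 makes the same commitment for failed attempts and also uses the All Implanted denominator.

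**The concern.** The plan expects some attempts to fail, because it defines an analysis set by attempt and promises tables for subjects without a full implant. It does not say how those subjects are observed after the procedure. Protocol 11.1 lists infection and wound complications such as hematoma and seroma as procedure risks, and such events may first appear days later. If the subject has already been exited, nobody is required to ask about them.

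The table for failed attempts could then look clean because observation had stopped, at the point where the procedure did not go as planned. Events that were never collected cannot be recovered at analysis.

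**Working it through.** The documents give no failed-implant rate and no figure on this point, so there is nothing to reproduce. The check compares what the protocol requires after each kind of procedure, then bounds the effect on the tables.

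**Step 1. Required contact by situation**

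| Situation | Required contact | Source |
|---|---|---|
| Successful implant | 7-day visit, then all visits to 24 months | Protocol 10.3, 10.14 |
| System modification with replacement | 7-day visit and 1-month call | Protocol 10.1, Table 4 footnote a |
| Explant, no replacement | 1-month call before exit | Protocol 10.1, 10.8 |
| Failed first attempt | None clearly stated | – |

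Explant without replacement is the closest comparison: a procedure in the leg that leaves no device in place. Its 1-month call was added in protocol version 3.0, with FDA feedback and risk-management review given as reasons (Version History). Section 10.8 also covers repeat attempts after an unsuccessful system modification, but has no counterpart for an unsuccessful first implant.

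**Step 2. Do the safeguards close the gap?**
- The recommendations in 10.14.1 and 12.3 apply to related events already ongoing or unresolved. They cannot reach an event that has not begun.
- The 48-hour call is recommended only, and it is unclear whether it applies when no implant was completed.
- Section 10.14 asks that related events continue to be reported after study participation until the product is explanted. A subject with no product in place is not clearly covered.

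What can be lost is therefore events with onset after exit, and ongoing events where the recommendation is not followed.

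**Step 3. Which tables are affected?**
- Main post-implant tables: the denominator is the All Implanted set (Protocol 14.9, SAP 7.10), so failed attempts do not dilute them.
- Additional FAS tables and failed-attempt summaries: affected.

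**Step 4. Largest possible size**

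Inputs: 121 completed implants (Protocol 14.7, SAP 6) and f failed attempts. The value of f is an assumption. Failure rates of 1% to 5% give 0.01 × 121 = 1.2 and 0.05 × 121 = 6.1, so about 1 to 6.

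Let x be the subjects with a recorded event and m the failed-attempt subjects whose only event was missed, with m at most f.
- Reported FAS percentage: x / (121 + f)
- Percentage with full collection: (x + m) / (121 + f)
- Understatement: m / (121 + f), at most f / (121 + f)

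| f (assumed) | FAS size | Largest understatement |
|---|---|---|
| 1 | 122 | 1/122 = 0.8 points |
| 2 | 123 | 2/123 = 1.6 points |
| 3 | 124 | 3/124 = 2.4 points |
| 5 | 126 | 5/126 = 4.0 points |
| 6 | 127 | 6/127 = 4.7 points |

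For illustration, with x = 12 (assumed) and f = 6, the reported figure is 12/127 = 9.4% and the full figure at most 18/127 = 14.2%, a gap of 6/127 = 4.7 points.

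In a table restricted to failed attempts the denominator is f, so the understatement is m/f and can reach the whole of the table.

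**The case against.** The case on the other side has several sound parts.

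- **Immediate exit is not directed.** A reader might infer that the protocol sends these subjects home and out of the study the same day. It does not: 10.14.1 urges subjects to stay as long as possible and says only that they may be exited. Same-day exit is the worst case that the wording permits.
- **Events up to exit are collected.** A reader might infer that all events after a failed procedure are lost. Sections 10.11 and 12.1 contradict this, and following known related events is recommended.
- **Some contact is recommended.** Table 4 marks check-in calls in the implant column, and footnote f is not limited to successful implants. The accurate statement is that no contact is clearly required.
- **The main safety rates are not diluted.** A reader might take SAP 7.1.3 to mean that failed attempts sit in the denominator of the main adverse event tables. SAP 7.10 says otherwise.
- **The number is small.** SAP 7.1.3 allows for the case where every implant succeeds. The upper bound needs every failed-attempt subject to have a missed event and no recorded one. No efficacy conclusion depends on it.
- **Other documents may help.** The consent materials and Clinician Guide are separate, and the opening of Protocol 12.5 was not in the text available. Either could contain a relevant instruction.

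All of this stands and limits the point. It does not supply an observation period after a failed attempt, and a recommendation to follow known events does not detect new ones.

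**Conclusion.** The point holds in a limited form. Under the protocol as written, a subject with a failed first attempt may leave the study with no minimum observation and no clearly required contact. Procedure-related events that start after exit would then be missing from summaries that both documents commit to produce.

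The understatement of an FAS subject-level percentage is at most about 0.8 to 4.7 percentage points. That range assumes 1 to 6 failures alongside 121 implants, with every failed-attempt subject having a missed event and no recorded one. The separate table of failed attempts could be affected throughout. The main post-implant tables and the efficacy objectives are not affected.

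A related inconsistency remains: SAP 7.1.3 calls the FAS primary for safety, while SAP 7.10 uses the All Implanted set for the main tables and the FAS for additional ones.

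**What to change.** 1. **Protocol 10.14.1 and Table 4 footnote a.** Keep not being implanted as a valid exit reason; removing it for failed attempts could leave these subjects without a listed reason to exit. Add that a subject with an attempted but unsuccessful implant stays under adverse event collection, counted from the attempt date, until the same 1-month post-procedure call already used after explant without replacement, and is then exited. Footnote a also names a 7-day visit, so the added text should say that the 1-month call is the contact that applies here.
2. **SAP 7.1.3 and 7.10.** Reconcile which set is primary for safety and which denominator each adverse event table uses.

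The cost is a wording change in each document and one call for a handful of subjects. The change concerns data collection only and leaves sample size, endpoints and testing as they are.

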10.14.2 Study Completed

At the completion of the 24-month follow-up visit, subjects will be exited from the study. The 24-month follow-up visit and exit visit should be combined, and both a 24-month follow-up visit eCRF and a Study Exit eCRF need to be completed.

11. Risks and Benefits

11.1 Potential Risks

The Clinical Study Risk Management process for the TITAN 2 Study is being performed in accordance with the Code of Federal Regulations for Investigational Device Exemptions (IDE) (21 CFR 812), FDA guidance, and elements of ISO 14971 applicable to clinical research studies to ensure that the level of risk is acceptable prior to starting the study.

The Medtronic TNM Clinician Guide and MRI Guidelines for the TNM Neurostimulator and associated TNM system labeling include system contraindications, precautions, warnings, adverse events, directions for use and other system specific details. In addition to the risks normally associated with a procedure, the following adverse events may occur with the use of an implantable neurostimulation system for tibial neuromodulation. Certain adverse events may necessitate surgical intervention.

Risks (potential adverse events) related to the tibial neurostimulator implant or explant procedure:

- Implant site pain
- Infection

- Reaction to local anesthetic (e.g., redness, irritation at the injection site)
- Wound complications (e.g., swelling, hematoma, bruising, bleeding, seroma)

Risks (potential adverse events) after implantation of the tibial neurostimulator:

- Adverse change in bowel and/or urinary function
- Allergic or immune system response to the implanted materials
- Device site pain
- Infection
- Neurostimulator migration or erosion
- Uncomfortable stimulation sensations

There may be technical device problems with the investigational system which could impact therapy delivery.

There is a possibility of risks to an unborn child. These risks are unknown. Women who are pregnant or expect to become pregnant during the course of the study are excluded from participating.

The clinical investigation has been designed to involve as little pain, discomfort, fear, and any other foreseeable risk as possible for the subjects, and both the risk threshold and the degree of distress are specifically defined in the clinical investigation plan and constantly monitored.

11.2 General Study Risk/Inconveniences

Subjects may find completing the urinary voiding diary and questionnaire embarrassing and/or an inconvenience.

As with all clinical research, there may be additional risks related to this study that are not yet known.

11.3 Risk Minimization

The potential risks associated with the TNM system and tibial neuromodulation were identified and have been successfully mitigated which include mitigations of selecting qualified investigators, training study personnel on the CIP and providing adequate instructions and labeling.

In addition, investigators will be actively involved in the implantation and follow-up of the subjects implanted with the TNM device. Risks will be minimized by careful assessment of each subject prior to, during, and after implant of the TNM system.

The subject will be informed of any potential study risks.

After implantation, subjects in the TITAN 2 Pivotal study will be followed at regular intervals to monitor the condition of the implanted device.

The Clinical Events Committee and Sponsor will review all related and serious adverse events and/or implantation at any time, if necessary, to protect the safety and well-being of subjects. The study will pause enrollment and implantation after 7 study subjects experience device migration that results in a device explant. This criterion corresponds to a rate of 6% (7/121) of the total planned implanted subjects and ensures that the final 90% confidence interval lower bound (2.7%) for the observed rate exceeds the previously reported rate of adverse events related to migration that led to device explant (2.2%)¹⁴.

Due to lack of reported data regarding adverse events related to erosion in this therapy space, a similar pausing criterion will also be applied for erosion that results in a device explant. That is, the study will pause enrollment and implantation after 7 study subjects experience device erosion that results in a device explant.

Should enrollment and/or implantation pause due to either of these rules (for device migration or erosion), the FDA will be notified. The study will not continue implanting until approval is obtained from the FDA.

11.4 Potential Benefits

The TNM system may offer no medical benefit. The potential benefits of having the TNM system may include an improvement in overactive bladder symptoms. Additionally, information collected from this study may assist in the design of new product(s)/therapy(ies), future clinical studies, and/or product labeling.

11.5 Risk-Benefit Rationale

Residual risks of the TNM system have been characterized as acceptable per Medtronic clinical procedure for risk management. No further risk mitigation is required at this time. Medtronic will continue to evaluate the risk/benefit profile, safety, and performance of the product as data becomes available.

The following measures will also be taken to minimize risk to participants as part of this clinical investigation plan:

1. Physicians and staff will receive appropriate training prior to using the study devices. Training will include instruction on the implant and explant procedure, TNM system and protocol requirements
2. Instructions are provided with the TNM device and study aids to ensure consistent use of the device within pre-tested parameters.
3. Subjects will be closely monitored by appropriately trained personnel during the procedure and at regularly scheduled intervals for the duration of the study where their comfort, any potential adverse events and satisfaction will be assessed.
4. Physicians will employ usual and customary clinical technique (e.g., sterile technique during implant use and aseptic wound care procedures).

5. Stimulation will be set in clinic with feedback from the study subject
6. All subjects will have the ability to turn off or adjust stimulation at any time using the provided handset and communicator.

In addition to the potential benefits to the subjects of the study in terms of an improvement in overactive bladder symptoms, the benefit of the study also lies in the knowledge to be gained from the TITAN 2 results and the potential to improve future TNM therapies. Based on the risk acceptance criteria for the TITAN 2 study outlined in the risk management documentation, the study-specific residual risk is determined to be acceptable given the expected benefits.

11.6 Risk Determination

The TNM system used in the TITAN 2 Pivotal study meets the definition for a significant risk (SR) investigational device exemption (IDE) study in 21CFR§812.3(m), because it is an implanted device and presents a potential for serious risk to the health, safety, or welfare of a subject.

12. Adverse Events and Device Deficiencies

12.1 Adverse Events

All adverse events as well as all device deficiencies will be considered reportable for this study and will be collected after the subject is consented to participate in the study through study exit. The term “investigational device” is part of ISO 14155:2020 definitions. The term “investigational device” refers to any device used in the study including market released devices.

Adverse event terms are defined as follows:

- Device Related: An adverse event that results from the presence or performance (intended or otherwise) of any component of the TNM system
- Procedure Related: An adverse event that occurs due to any procedure related to the implantation or explant of the TNM system. The procedure is defined as the neurostimulator implant and/or explant procedures
- Study Aids Related: An adverse event that results from the presence or performance (intended or otherwise) of any study aids related to the TNM system
- Therapy Related: An adverse event related to therapy delivery by device e.g., device stimulation issue (normally therapy-related events resolve when the device is turned off or reprogrammed).

Adverse events that are classified as possible, probable, or causal are considered to be related for analysis purposes. Reporting of adverse events to Medtronic will occur on an AE eCRF. Each event must be reported separately. For AEs that require immediate reporting (see Table 10: Reporting Requirements), initial reporting may be done by phone or on the eCRF completing as much information as possible. The completed AE eCRF must be submitted to Medtronic as soon as possible.

Any medication/treatment associated with the treatment of an AE must be reported.

Subject deaths are also required to be reported in accordance with Table 10: Reporting Requirements.

All non-subject AEs (users or other persons as defined in Table 6) will be collected throughout the study duration.

Special considerations for adverse events and device deficiencies reporting:

- Normal expected complaints or symptoms reported during or following the procedure which are related to ordinary procedure or post-procedure care will be reported as adverse events; however, they will not be analyzed as device, procedure, therapy, or study aid-related adverse events unless there is a clinically significant change in severity or duration of symptoms, or the event requires clinical intervention that is different from ordinary procedure or post-procedure care.
- Includes headache, incisional pain, nausea, vomiting, low grade fever, oozing at dressing, dizziness, irritability, sleepiness, nervousness, insomnia, constipation, confusion, skin irritation/redness, and similar events.
- The Clinical Events Committee will review these events to confirm agreement with the decision made by the study investigator.
- Any non-clinically significant stimulation-related effects that occur during the implant procedure, programming, and follow-up period will not be considered a reportable adverse event.
- Worsening of OAB symptoms (including questionnaire outcomes) will be collected as part of the efficacy objectives and will not be considered a reportable adverse event.
- Device movement should be assessed and reported as an adverse event if there is clinically significant pain, loss of nerve capture resulting in loss of efficacy, or device explant
- Documented pre-existing conditions are not considered AEs unless the nature or severity of the condition has worsened.
- It is recommended that additional diagnostic information be collected to evaluate reported adverse events, such as suspected infections. It is recommended that cultures are obtained prior to antibiotic treatment for any suspected infections with discharge or that result in device explant procedures. Additional diagnostic information should be reported on the Adverse Event eCRF.

